### 5.3.1 Patient Randomization

Details of patient randomization are described in the Operations Manual.

[name], the NCI statistician, will generate randomization assignment sheets. The sheets will be based on a stratified randomization, which will be created using software that generates randomized blocks of varying sizes as directed by [name]. He will provide these sheets directly to the SARC Operations Office, where they will be maintained in a confidential manner.

After the patient is registered and enrolled electronically by the site through the SARC study website, the site will contact the SARC Operations Office to obtain patient randomization treatment assignment.

The site pharmacy will be notified of the assigned randomization treatment (i.e. saracatinib or placebo). After confirmation of receipt of treatment assignment by the site pharmacy, labeled, blinded medication will be dispensed for the patient. This will consist of saracatinib in 125 mg and 50 mg tablets, or placebo 125-like and 50-like tablets, in accordance with the protocol.

The randomization assignment should be kept confidential and should not be shared with the treating physician(s) or any other site team staff involved in the care of the patient, except in the event of a medical emergency where unblinding is necessary for patient care (see section 7.4) or for disease recurrence (see section 7.4.2)

### 5.4.1 IRB Approvals

The protocol must be approved at the participating institution prior to enrolling patients. Documentation of individual institutional IRB approval for the current protocol must be sent to SARC along with IRB approved consent.

### 5.4.2 Amendments and Consents

Institution informed consent form must be sent to SARC for review and approval prior to submission to their IRB. All amendments must be submitted to institutional IRB for review and approval. Documentation of approval of amendments and of yearly continuing review must be sent to SARC to permit site continued enrollment and treatment of patients on this study.

### 5.4.3 Data Collection and Toxicity Reporting

Weekly registration and reports will be generated by SARC to monitor patient accrual and completeness of registration data. Routine data quality reports will be generated to assess missing data and inconsistencies by the Research Project Manager at SARC.

A monthly telephone conference will be held between the study Principal Investigator and the research project manager at SARC to address any issues that arise pertaining to this study.

Unexpected CTCAEv3 grade 3 or grade 4 toxicities (see Section 8.1.5 for known toxicities of saracatinib) and all grade 5 toxicities must be reported to the research project manager at SARC within 24 hours of the occurrence (see Section 7.3.1). All serious adverse events will be submitted to the National Heart, Lung and Blood Institute (NHLBI) IRB (see Section 7.3.2).

#### 5.4.4 Data and Participating Institution Audits

SARC research project manager will review data entered into the electronic data capture system on a weekly basis and generate queries as needed. No on site audit will be performed for this study. Selected source documents will periodically be requested by SARC for verification of data entered into the electronic data capture system. All source documents submitted to SARC will be marked with the patient initials and patient unique study number. All other patient identifiers will be redacted.

### 5.5 Data and Safety Monitoring Plan

The SARC Executive Committee will convene monthly via teleconference to review with the study principal investigator the study accrual, adverse events, serious adverse events, protocol violations and/or deviations. Data provided to this committee will be blinded as to the treatment arm for the events reported. Any concerns related to patient safety will be referred to the NCI DSMB as they will have access to unblinded data.

A NCI-created DSMB will monitor this trial for toxicity, as well as clinical endpoints relative to early termination, in its annual meetings. As noted above (see Section 5.3), clinical evaluations of endpoints will be formally evaluated beginning after 40 to 60 total patients have accrued and potentially followed for 12 months.

## 6 Human Subjects Protections

### 6.1 Rationale for Subject Selection

Subjects of both genders and from all racial and ethnic groups are eligible for this trial if they meet the eligibility criteria (see Section 2.1). No groups are being excluded from participation in this trial. To date, there is no information that suggests differences in the effectiveness of saracatinib between genders or among racial or ethnic groups in any patient with cancer, indicating that the results of this trial will be applicable to all groups. Efforts will be made to extend the accrual to a representative population. Patients with recurrent osteosarcoma are rare and our hope is to enroll every patient in the United States. Since recurrent osteosarcoma affects both genders and all racial and ethnic groups, almost equally, this trial should be composed of a representative population. All participating institutions will need to have IRB approval prior to registering a subject for this trial.

### 6.2 Participation of Children

Pediatric subjects  $\geq 15$  years of age are eligible for this trial. Patients with recurrent osteosarcoma are typically adolescents or older. Until the safety/efficacy of this approach is established, children  $< 15$  years of age will not be included in this study.

### **6.3 Evaluation of Benefits and Risks/Discomforts**

The primary risk to patients participating in this research study is from toxicity of anticancer drugs and the agents used to alleviate the toxicities of the anticancer drugs. For patients with recurrent osteosarcoma, there is no salvage regimen that offers a good response rate. The current standard of care is to resect all recurrent nodules, if this is possible. The primary objective of this study is to assess the ability of saracatinib, versus placebo, to increase progression free survival in patients who have undergone complete resection of recurrent nodules. Saracatinib has been tolerated in patients with advanced cancers, but it is still an investigational agent. As such, an additional risk to patients participating in this trial may be that saracatinib may have an increased incidence of side effects. Potential benefits for patients who participate in this study include a possible increase in progression free survival. Since the standard of care is surgical resection, patients who are randomized to receive placebo, will be receiving the standard of care.

The medical, hospital and research records associated with this study are considered confidential. Members of the treating team and designated research study assistants will have access to the records as required to administer treatment and comply with the protocol. Neither the name nor other identifying information for an individual will be used in any reports or publications concerning this study. Patient records may be inspected by auditing agencies, including the NCI, the FDA, SARC (the study sponsor) and AstraZeneca (the distributor of saracatinib) to satisfy regulatory requirements.

### **6.4 Risks/Benefits Analysis**

This protocol provides for detailed and careful monitoring of all patients to assess for toxicity and response to treatment. Patients will be treated with therapeutic intent and response to the therapy will be closely monitored. The potential benefit from this therapy is to improve progression free survival. Therefore, this protocol involves greater than minimal risk to subjects, but presents the potential for direct benefit to individual subjects.

### **6.5 Consent and Assent Processes and Documentation**

A signed informed consent document will be obtained prior to entry onto the study. The investigational nature and research objectives of this trial, the procedures and treatments

involved and their attendant risks and discomforts and potential benefits, and alternative therapies will be carefully explained to the patient and/or the patient's parents or guardians if she/he is a child. The investigators are requesting a waiver from the NCI IRB to allow only one parent or guardian to sign the informed consent to enter a child on the protocol. Because many patients must travel to the NIH from long distances at substantial expense, requiring both parents to be present for the consent process may adversely impact other children at home and pose financial hardship due to loss of work-related income. Other participating centers will have patients in similar circumstances and may request a similar waiver from their IRB.

The institutional Principal Investigator, or their designee, will meet with the patient, or the patient's parents or guardian, and other family members, to discuss the protocol treatment and alternative options. It will be stated clearly that participation in the research study is voluntary and that participants can withdraw from the study without losing benefits they would otherwise be entitled to. The patient and family members will be encouraged to ask questions, and additional meetings to discuss the treatment options will be arranged if necessary. The institutional Principal Investigator, or their designee, will then obtain consent from the patient. For patients who are <18 years of age, where deemed appropriate by the clinician and the child's parents or guardian, the child will also be included in all discussions about the trial and verbal or written assent will be obtained. The parent or guardian will sign the designated line on the informed consent form attesting to the fact that the child has given assent.

## **6.6 Handling of Research Samples**

This study is being conducted and coordinated by SARC. Collection of blood can occur any time prior to the first dose of oral therapy. A blood specimen should be collected regardless of whether there is tissue to be submitted. Collection of tumor tissue for research purposes will occur at the time the tumor is resected (see Sections 3.6.1 and Operations Manual). A corresponding H+E should also be prepared and sent to the NIH. Every attempt will be made to obtain tissue samples and to combine the collection of research samples with the collection of specimens for clinical care purposes. If there is not a tissue sample available the patient is still eligible to participate in the trial. Research specimens will be evaluated for the following:

- Microarray analysis (for all patients)
- Biomarkers related to activation of Src and Src substrates (for NIH patients)
- Establishment of cell lines and murine xenografts (for NIH patients)
- Sequencing analysis (for all patients)

Samples will be transported in a manner that complies with current regulatory guidelines for transport of specimens. All samples will be labeled with a protocol-specific patient tracking number that was generated for the patient at the time of randomization. Sample labeling, collection and initial processing will be conducted as described in the Operations Manual. Unintentional loss or destruction of any sample will be reported to the National Cancer Institute (NCI) IRB and the IRB of the responsible Institutional

Principal Investigator as part of annual continuing reviews. Unexpected problems such as, but not limited to, natural disaster, equipment malfunction, and human error, will be reported to the IRB in written form. Any use of these samples for purposes not described in this section will require prospective NCI IRB review and approval.

For all fresh frozen tumor samples submitted, microarray studies and corresponding normal lymphocytes will be performed in the laboratory of [name] (see Sections 3.6.1 and Operations Manual for details). Participating institutions are requested to send fresh frozen tissue, a corresponding H+E slide, and peripheral blood to the NIH. Samples will be tracked and considered the responsibility of the Institutional Principal Investigator, until they are received by the designated recipient at the NIH. Samples will then be logged into a database on a secured computer. Tumor samples will be stored in a designated monitored -80°C freezer. Peripheral blood will be processed for isolation of white blood cells which will then be stored in a designated monitored -80°C freezer associated with [name] laboratory until analyzed. After the samples have been analyzed and the results published, any remaining samples will be transferred anonymously to a research sample protocol. To maintain the integrity of the blind, at no point, will clinical investigators have access to the results of these studies.

For all fresh frozen tissue samples received from patients who are treated at the NIH, activation of Src and Src substrates will be determined by immunohistochemistry in the laboratory of [name] (see Sections 3.6.2 for details). Samples will be logged into a database on a secured computer, and stored at room temperature and secured in [name] laboratory. After the samples have been analyzed and the results published, any remaining samples will be transferred anonymously to a research sample protocol. To maintain the integrity of the blind, at no point, will clinical investigators have access to the results of these studies.

For all tissue samples received from patients who are treated at the NIH, tumor samples will be minced and cultured in media in an effort to obtain a stable cell line in the laboratory of [name] (see Sections 3.6.3 for details). These samples will only be obtained if extra samples are available. Sterile resection samples are sent to pathology. After samples are sent for clinical analysis and other requirements of this protocol, any extra tumor samples will be added sterilely into a 50 cc conical tube containing 20 ml of tissue culture media. The sample will be minced and added to a tissue culture flask containing tissue culture media. Samples will then be logged into the NCI LabMatrix database on a secured computer. Tissue culture samples will be propagated in a tissue culture incubator associated with [name] laboratory. In most cases, a cell line will not result and the sample will be destroyed. In the rare event that a cell line does result, the cell line will be renamed in the following format (NCI-OST-last two digits of the year-random one digit check number). The cell line will then be aliquoted and frozen in liquid nitrogen. Two aliquots will be deposited with ATCC with only the renamed identifier and the following description: "recurrent osteosarcoma tumor isolated from the lung." At no point will any other clinical information be given to ATCC. Although it will be impossible to determine the type of treatment that a patient is receiving based these results, at no point will clinical investigators have access to the results of these studies.

For all tissue samples received from patients who are treated at the NIH, tumor samples will be minced and injected into immuno-compromised mice to obtain xenografts in the laboratory of [name] (see Sections 3.6.3 for details). These samples will only be obtained if extra samples are available. Sterile resection samples are sent to pathology. After samples are sent for clinical analysis and other requirements of this protocol, any extra tumor samples will be added sterilely into a 50 cc conical tube containing 20 ml of tissue culture media. The sample will be minced and added to a tissue culture flask containing tissue culture media. Samples will then be logged into the NCI LabMatrix database on a secured computer. Tissue culture samples will be propagated overnight in a tissue culture incubator associated with [name] laboratory. The following day, tumor samples will be surgically implanted in the area of the tibia. In most cases, a primary tumor will not form and the mouse will be euthanized. In the rare event that a primary tumor does form, the resulting tumor will be renamed in the following format (XEN-OST-last two digits of the year-random one digit check number). The tumor will be harvested, minced and frozen in liquid nitrogen. Although it will be impossible to determine the type of treatment that a patient is receiving based these results, at no point will clinical investigators have access to the results of these studies.

For all patients for whom frozen tissue is available, sequencing analysis of DNA and RNA from tumor samples and corresponding normal lymphocytes will be performed in the laboratory of [name]. This will include transcriptome sequencing, exon re-sequencing and mate-pair end sequencing. These studies will be performed on material that is left over following microarray analyses (see Sections 3.6.1, 6.6 and Operations Manual for details). The logistics have been described previously.

## 7.2 Adverse Event Recording

### 7.2.1 Definitions

**ADVERSE EVENT:** An adverse event (AE) is any untoward medical occurrence associated with the use of a drug in humans, whether or not considered drug related. An adverse event can therefore be any unfavorable and unintended sign (including an abnormal laboratory finding), symptom, or disease temporally associated with the use of a medicinal (investigational) product, whether or not the event is considered causally related to the use of the product. Such an event can result from use of the drug as stipulated in the protocol or labeling, as well as from accidental or intentional overdose, drug abuse, or drug withdrawal. Any worsening of a pre-existing condition or illness is considered an adverse event.

**Life-threatening adverse event or life-threatening suspected adverse reaction:** An adverse event or suspected adverse reaction is considered "life-threatening" if, in the view of either the investigator or sponsor, its occurrence places the patient or subject at immediate risk of death. It does not include an adverse event or suspected adverse reaction that, had it occurred in a more severe form, might have caused death.

**SERIOUS ADVERSE EVENT OR SERIOUS SUSPECTED ADVERSE REACTION:** A serious adverse event (SAE) is considered 'serious' if, in the view of the investigator or sponsor it results in any of the following outcomes:

- Death
- is life-threatening
- requires inpatient hospitalization, or prolongs an existing hospitalization
- causes persistent or significant incapacity or substantial disruption of the ability to conduct normal life functions
- results in congenital anomalies or birth defects
- Important medical events which in the judgment of the investigators may jeopardize the patient and may require medical or surgical intervention to prevent one of the outcomes listed in this definition.

**SUSPECTED ADVERSE REACTION:** Any adverse event for which there is a reasonable possibility that the drug caused the adverse event. For purpose of safety reporting, "reasonable possibility" means there is evidence to suggest causal relationship between the drug and the adverse event. **SUSPECTED ADVERSE REACTION** implies a lesser degree of certainty about causality than adverse reaction, which means any adverse event caused by a drug.

**EXPECTED ADVERSE EVENT:** An expected adverse event (EAE) is an adverse event with a non-fatal outcome that is described in section 5.4 of the Investigator's Brochure or in section 8.1.5 of this protocol.

**UNEXPECTED ADVERSE EVENT:** An unexpected adverse event (UAE) is any adverse event that is not described at the specificity and severity that has been observed and described in section 5.4 of the Investigator’s Brochure or in section 8.1.5 of this protocol, or an event described in these sections that has a fatal outcome.

**ATTRIBUTION:** The relationship of adverse events to the study medication will be assessed by means of the question: “Is there a reasonable possibility that the event may have been caused by the study medication?” The Institutional Principal Investigator will answer: Yes or No. If there is a reasonable possibility that the event is related to study drug, then Yes would be designated for causality to study drug. If there is clearly no possibility that the event is related to the study drug then No would be designated for causality to study drug.

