different treatments, including surgery alone, and/or radiation, and/or chemotherapy, and/or high dose chemotherapy with stem cell rescue. Therefore, historical data do not give a true indication of actual survival rates. This study will try to determine whether patients who receive saracatinib will experience a 60% relative increase in progression free survival. Secondary objectives will determine whether patients who receive saracatinib will experience a 56% relative increase in overall survival and an increase in the time to treatment failure. Any adverse event, including toxicity, disease progression and death, that result in discontinuation of either saracatinib or placebo will be considered a treatment failure. The randomized nature of this study will allow us to determine the actual survival rates in these two cohorts, thereby assessing the efficacy of saracatinib in this patient population. Forty-four patients will need to be randomized in each arm, for a total of 88 patients, over a 48-month accrual period. Follow-up for survival of the last patient randomized must continue for an additional year. Patients who recur in the lung while on-study and who are thought to be amenable to complete surgical resection will be unblinded. Those who were receiving placebo will be given the option of undergoing surgical resection. If fully resected, they will be given the option to begin oral therapy with saracatinib.

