### 3.2.6 Cross-over Regimen for Patients Who Recur in the Lung While On-Study

Patients who recur in the lung while on study, and who are thought to be amenable to complete surgical resection of the recurrent tumor will be unblinded. Those patients who were receiving placebo will then have the option of undergoing surgical resection; if fully resected they will be given the option to begin oral therapy with Saracatinib.

Saracatinib will be administered as a once daily, oral dose of 175 mg, for a 28-day cycle, with no breaks between cycles. The duration of treatment with saracatinib will be thirteen 28-day cycles (364 days total). Cycle 1 Day 1 must commence no later than 6 weeks after the time of the definitive metastasectomy. Patients who cannot commence oral therapy within 6 weeks will be removed from the study.

Biological studies to determine the etiology of recurrent osteosarcoma are an important component of this protocol. Prior to metastasectomy, every attempt should be made to

insure that the tumor sample is handled properly, so that all of the biological studies can be performed (see Sections 3.6.1 and Operations Manual).

Patients who recur in locations other than the lung while on-study will be taken off study and will not be unblinded.

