#### **Initial notification of serious adverse events**

The treating physician or other site personnel must report all serious adverse events within 24 hours to the study coordinator at SARC.

All SAEs must be reported, whether or not considered causally related to the investigational product or to the study procedure/s. All SAEs will be recorded in the CRF.

All serious AEs (SAEs), whether considered related or unrelated to investigational product, must be reported immediately (**within 24 hours of awareness**) by the investigational site to SARC, the Study Principal Investigator, and AstraZeneca Patient Safety by confirmed facsimile transmission. If only limited information is initially available, follow-up reports are required. The original SAE form must be kept on file at the study site.

SAEs should be reported on the MedWatch Form 3500A, which can be accessed at: <http://www.accessdata.fda.gov/scripts/MedWatch/>. The MedWatch form must be completed using the following guidelines:

- The date the site notified SARC and AstraZeneca of the SAE must be specified in the “Describe event” narrative section.
- Initial and follow-up MedWatch reports should be numbered either in the narrative section or in section G.7 of the MedWatch form.
- If more than one SAE is listed on the MedWatch form, each event should be numbered.
- Institutional Principal Investigator must designate causality to study drug for each SAE and must be specified in both the “Describe event” narrative section of the MedWatch form and the SARC012 SAE Fax Coversheet.
- There will be 2 causality designations: Yes = Related to study drug, No = Unrelated to study drug
  - If there is any possibility that the SAE is related to study drug, then designate Yes for causality.
  - If there is clearly no possibility that the SAE is related to study drug, then designate No for causality.
- If the SAE is considered to be related to a study procedure, this should also be indicated in the narrative section

For all SAEs, completed MedWatch forms along with a completed SAE Fax Coversheet (Appendix C) should be faxed to SARC, the Study Principal Investigator, and AstraZeneca Patient Safety **within 24 hours** of awareness of the event. The SAE Fax

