### 7.4.1 Criteria for Unblinding for Serious Adverse Events

The following events require unblinding of treatment assignments in this study:

1. The occurrence of a serious adverse event that is both unexpected and considered by the reporting investigator to be associated with the use of study drug, and the knowledge of the treatment assignment is deemed essential for the patient's care.
2. An unexpected serious adverse event occurs and the intervention must be made known for purposes of reporting to the FDA (SARC responsibility as Study Sponsor).

Unblinding of treatment assignments for patients on this study will be performed by authorized SARC personnel, upon approval from the SARC Medical Officer or designee.

Requests for unblinding by the site should be only for urgent patient safety issues.

**Note: To ensure patient safety, if need be, all discussions can be done verbally with written documentation to follow once patient safety secured.**

Any patient whose treatment assignment is unblinded because of a serious adverse event(s) will be removed from study treatment and followed only for survival. The site should continue to follow the patient status regarding the serious adverse event(s) for which the patient's treatment was unblinded until resolved or improved to baseline and the patient can receive additional off-study treatment as necessary.

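### Osteosarcoma recurrence, the primary endpoint event, is not exempted from the adverse event and SAE definitions, so an all-cause SAE count by arm would partly re-count efficacy

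*Combined protocol and SAP*

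**What the plan says.** Section 7.2.1 defines an adverse event broadly and adds: "Any worsening of a pre-existing condition or illness is considered an adverse event". Section 7.2.2 requires recording regardless of suspected cause, from consent to 30 days after the last dose, and includes exacerbations of existing illness. Section 1.2.9 describes treatment failure as "Any adverse event, including toxicity, disease progression and death" leading to discontinuation. Sections 3.7.1 and 5.3 likewise list progression among the adverse events that count as treatment failure. Section 3.7.1 defines progression as recurrence of osteosarcoma.

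Under 7.2.1 an event is serious if, in the view of the investigator or sponsor, it results in death or "requires inpatient hospitalization, or prolongs an existing hospitalization", among other criteria. Section 3.7.1 asks for resection to be attempted in any patient who recurs. Section 7.3.1 adds: "All SAEs must be reported, whether or not considered causally related to the investigational product". Recurrence is not on the expected list in section 8.1.5, and an event on that list becomes unexpected if it is fatal ("or an event described in these sections that has a fatal outcome").

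On review of these data, section 5.5 says: "A NCI-created DSMB will monitor this trial for toxicity". It gives that board unblinded data. Section 5.3 plans no safety table and does not separate recurrence from other SAEs.

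**The concern.** An SAE comparison should show what the drug does apart from its effect on the tumour. If recurrences that lead to admission or death are counted as SAEs, a drug that prevents recurrence lowers its own SAE count, and that reduction can offset a real excess of drug-caused events. If the drug has no effect on PFS, recurrences add similar numbers to both arms and make a real excess harder to see. The primary PFS test is unaffected. What is at stake is the toxicity picture that the DSMB sees and that would inform the definitive trial anticipated in section 1.2.9.

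**Working it through.** **Inputs from the documents.** Hazards of 0.0462 (placebo) and 0.0265 (saracatinib) per month, 44 patients per arm, 48 months' accrual plus 12 months' follow-up, and one-sided alpha 0.10 (section 5.3). Treatment lasts 364 days (section 3.1). Adverse events are collected to 30 days after the last dose (section 7.2.2).

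**Reproducing the plan's figures.** -ln(0.33)/24 = 0.0462 and -ln(0.53)/24 = 0.0265, a ratio of 1.75. One-year PFS is 57.4% and 72.8%, as stated. Expected events per arm are 44 × [1 - (e^(-12h) - e^(-60h))/(48h)], 59.7 in total. Power is 80.8% by Schoenfeld's formula and 79.3% by Freedman's, against the stated 80%. The plan gives no SAE rate to reproduce.

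**Recurrences in the collection window**, 1 - e^(-h × months), treating every PFS event as a recurrence:
- Day 364 (11.96 months): 42.4% and 27.2%, or 18.7 and 12.0 of 44.
- Day 394 (12.94 months): 45.0% and 29.0%, or 19.8 and 12.8 of 44, a gap of about 7 patients.

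Day 394 is an upper bound. The 30 days run from each patient's own last dose, and after the end-of-treatment scan the next scheduled CT is at month 18 (section 3.4).

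**Assumptions not in the documents.** Let s be the share of recurrences that become serious and t the risk of a non-tumour SAE. I take t = 5% on placebo and 15% on saracatinib, independent of recurrence, and vary s from 0 to 100%. The risk of at least one SAE is 1 - (1 - t)(1 - s × recurrence share). For s = 50%:
- Placebo: 1 - 0.95 × (1 - 0.5 × 0.450) = 26.4%.
- Saracatinib: 1 - 0.85 × (1 - 0.5 × 0.290) = 27.3%.

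The chance of no visible excess is the probability that saracatinib has no more patients with an SAE than placebo, from two independent binomials with n = 44. Results to day 394:

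| s | Placebo | Saracatinib | Difference (points) | Chance of no excess | Same, if no PFS effect |
|---|---|---|---|---|---|
| 0% | 5.0% | 15.0% | +10.0 | 8% | 8% |
| 10% | 9.3% | 17.5% | +8.2 | 16% | 12% |
| 25% | 15.7% | 21.2% | +5.5 | 30% | 18% |
| 50% | 26.4% | 27.3% | +1.0 | 51% | 25% |
| 75% | 37.1% | 33.5% | -3.6 | 68% | 30% |
| 100% | 47.8% | 39.7% | -8.1 | 81% | 34% |

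The last column gives both arms the placebo hazard. The difference then keeps its sign and shrinks only to +5.5 points at s = 100%.

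**Sensitivity.** Stopping at day 364 gives 16%, 29%, 49%, 66% and 79% for s = 10% to 100%. With true risks of 5% and 20%, the chance of no excess is 2% at s = 0, 15% at s = 25% and 70% at s = 100%. At a 5% placebo risk, the true drug excess that recurrence would fully cancel is about 4, 9, 15 and 21 points at s = 25%, 50%, 75% and 100%.

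**The case against.** The strongest reply is that section 7.2.1 governs what is collected, not how it is tabulated. Three stronger readings are tempting, and the documents do not support them.

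- **A reader might infer that the DSMB judges toxicity by comparing all-cause SAE rates between arms.** No such comparison, pooled rate or safety boundary is written. Each SAE carries a term, a grade and a causality judgement (sections 7.2.2 and 7.3.1, Appendix C), so an unblinded board could set recurrences aside. This stands, and it confines the point to any all-cause count that is produced. Separation by attribution is only partial, because the threshold for a positive answer differs between 7.2.1 (a reasonable possibility) and 7.3.1 (any possibility).
- **A reader might infer that every recurrence becomes an SAE.** Seriousness is a judgement, and the admission or death must fall within a short window. Patients whose recurrence is outside the lung or unresectable, and all saracatinib patients who recur, come off study. The Precis defines time to treatment failure without calling progression an adverse event, and the removal criteria list progression apart from toxicity. Values of s near 100% are therefore implausible, and the low values in the table matter.
- **A reader might infer that 7.4.1 item 2 contradicts the blinding rule for recurrence.** Section 3.2.6 says "Patients who recur in locations other than the lung while on-study will be taken off study and will not be unblinded", while item 2 applies where "An unexpected serious adverse event occurs and the intervention must be made known for purposes of reporting to the FDA". The first concerns recurrence and cross-over. The second is unblinding by the sponsor for regulatory reporting, and it would apply only if a recurrence were coded drug-related and then judged reportable. That is at most a point to reconcile.

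Two further limits stand. Section 7.3.1 places the full SAE procedures in a Safety Reporting Plan that was not supplied, so an exemption may exist there. It would still have to be squared with the wording in 1.2.9, 3.7.1, 5.3 and 7.2.1. Also, if PFS improves, saracatinib patients stay on drug longer and are observed longer for adverse events, which pushes their count the other way.

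**Conclusion.** The point holds in a limited form. On the supplied text, recurrence is an adverse event, and an SAE when judged to have led to admission or death. An all-cause SAE count by arm would therefore partly re-count the primary endpoint, and no planned table separates the two. The recurrence shares follow from the protocol's own hazards. The distortion does not: it depends on an assumed share of serious recurrences, assumed non-tumour risks, independence, and the full hypothesised PFS effect being real. Under those assumptions it is small if 10% of recurrences become serious, removes about half of a 10-point excess at 25% and nearly all of it at 50%. Without a PFS effect, recurrence dilutes the comparison but does not favour either arm. This is an inexpensive improvement to safety reporting, not a flaw in the primary analysis.

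**What to change.** In section 7.2.1, state that recurrence or progression of osteosarcoma, and admission or death due solely to it (including admission for planned re-resection), is recorded as an efficacy outcome and not as an AE or SAE. State equally that complications of that surgery, and any event with a suspected drug contribution, remain AEs or SAEs. An uncertain pulmonary event should stay in, because pneumonitis is an expected toxicity (section 8.1.5) and the tumour recurs in the same organ.

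If inclusive capture is preferred, the minimum is to tabulate SAEs by arm with and without recurrence, for the DSMB and the final report. Under either option, list all-cause deaths and all admissions by arm. Reword 1.2.9, 3.7.1 and 5.3 so that progression is a treatment failure but not an adverse event, and check the result against the Safety Reporting Plan. Clarify how 7.4.1 item 2 relates to 3.2.6 and 7.4.2.

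The cost is a paragraph of wording and a table specification, and the exemption would reduce SAE paperwork. The downside is that a drug-caused admission or death could be misattributed to tumour and leave the SAE stream. The listings of deaths and admissions by arm are there to keep such events visible.
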